8 SELECTION AND WITHDRAWAL OF PATIENTS

8.1 Screening Inclusion Criteria

Patients may be randomized to the study only if they meet all of the following criteria at screening:

- 1- Subjects must exhibit symptoms (including at least one lower respiratory symptom such as shortness of breath or dyspnea) of COVID-19 disease at screening and/or since the start of their hospitalization (may include treated symptoms);
- 2- Subjects must be 18 years and older, of either gender;
- 3- Subjects must have at least one of the following factors/co-morbidities:
 - a) Controlled or uncontrolled diabetes;
 - b) Pre-existing cardiovascular disease, including hypertension;
 - c) Pre-existing respiratory disease such as COPD, asthma, emphysema;
 - d) Active or a former smoker with a 20 pack-years of smoking history;
 - e) Obesity as depicted by BMI>30;
 - f) Laboratory tests indicative of a higher risk of COVID-19-related complications, such as troponin >1.5 ULN, D-dimer >3.0 ULN and/or CRP >1.5 ULN
 - g) Patient aged 70 years and older who, based on the judgment of the Investigator, is at a higher risk of developing complications.
- 4- Subjects must have a documented positive test for the SARS-CoV-2 virus (co-infection with other viral respiratory infections is allowed and must be documented in medical history);
- 5- Subjects must be under observation by, or admitted to a controlled facility or hospital and receive SOC for COVID-19 disease;
- 6- Subject's health status must be 3 or 4 on the Ordinal Scale and not previously a "5 or a 6";

- 7- If female, must be either post-menopausal (one year or greater without menses), surgically sterile, or, for female subjects of child-bearing potential who are capable of conception must be: practicing a highly effective method of birth control (acceptable methods include intrauterine device, complete abstinence, spermicide + barrier, male partner surgical sterilization, or hormonal contraception) during the study and through 30 days after the last dose of the study medication. Periodical abstinence is not classified as an effective method of birth control. A pregnancy test must be negative at the Screening Visit;
- 8- Subjects must have the ability to understand and give informed consent, which can be verbal with a witness, according to local requirements;
- 9- Subjects deemed capable of adequate compliance including attending scheduled visits for the duration of the study;
- 10-Subjects must be able to swallow the study drug capsules.

8.2 Screening Exclusion Criteria

Patients are to be excluded from the study at the time of screening for *any* of the following reasons:

- 1. Pregnancy or breastfeeding;
- 2. Health condition deemed to possibly interfere with the study endpoints and/or the safety of the patients. For example, the following conditions should be considered contraindicated for participation in the study, but this is not an exhaustive list. In case of doubt, the Investigator should consult with the Sponsor's medical representative:
 - a) Presence of inherited retinitis pigmentosa;
 - b) Presence or history of liver failure (Child-Pugh B or C);
 - c) Presence or history of stage 4 severe chronic kidney disease or dialysis requirement;
 - d) Febrile neutropenia;
 - e) Presence of end-stage cancer;
- 3. Known history of a severe allergy or sensitivity to retinoids, or with known allergies to excipients in the oral capsule formulation proposed to be used in the study;
- 4. Participation in another drug clinical trial within 30 days (or a minimum of 5 elimination half-lives) prior to screening, except ongoing participation in non-interventional studies;
- 5. Calculated creatinine clearance (CrCL, using the Cockroft-Gault equation for example) <30 ml/min²;
- 6. Presence of total bilirubin >1.5 x ULN (in the absence of demonstrated Gilbert's syndrome), ALT and/or AST > 2.5 x ULN;
- 7. Patient expected to be transferred to ICU or die in the next 24 hours.

8.3 Study Drug Discontinuation and Withdrawal of Patients

Patients should discontinue permanently the study drug in the event of any of the following (Since a low LAU-7b dose is used in this study, no dose reductions are planned):

- 1. If a patient is escalated to invasive mechanical ventilation preventing the administration of the study medication intact;
- 2. Occurrence of a SAE deemed related to the study drug that is a life-threatening adverse reaction or one resulting in prolonged non-COVID-19 disease-related hospitalization;

LAU-7b for the treatment of COVID-19 disease in Adults

² When a factor that may potentially affect renal function by hemodynamic mechanisms is known or suspected on admission (Ex: dehydration), it is recommended to rule out a possible renal impairment by addressing the issue whenever possible (Ex: rehydration) and reassessing CrCL prior to signing the ICF.

- 3. If the patient, Investigator, or Laurent determines that it is not in the best interest of the patient to continue treatment;
- 4. If a patient is serially and persistently noncompliant with study procedures and/or assessments, the investigator or the sponsor may withdraw the patient from further treatment;
- 5. A patient's treatment is unblinded by the Investigator;
- 6. If a female patient has a confirmed pregnancy (with the exception of a pregnancy resulting from *in-vitro* fertilization), this should be immediately reported to the Medical Monitor and Laurent Pharmaceuticals (within 24 hours awareness) and the patient shall discontinue the study drug. Pregnancy, whether in a patient or in a partner of a patient should be followed up until conclusion, with an assessment of child health at birth:
- 7. Considering the safety observed so far in the study, patients showing possible kidney impairment as depicted by either:
 - a. An increase from screening in serum creatinine of 0.5 mg/dL or 2x the screening value if the serum creatinine was within normal range at screening and the calculated CrCL was \geq 30 ml/min;
 - b. An increase of serum creatinine $\geq 2x$ the screening value if the screening value was above the normal range and the calculated CrCL was ≥ 30 ml/min.
- 8. Notwithstanding that the study so far confirms the lack of a particular drug-related liver toxicity, patients showing possible liver impairment as assessed with the liver safety algorithm based on the Drug Induced Liver Injury (DILI) algorithm, described in Section 11.4
- 9. As soon as the site is informed, patients missing two consecutive doses or more than two non-consecutive doses at any point during the treatment period.

Patients withdrawn from further treatment but agreeable to provide outcome information should continue to undergo the safety and efficacy assessments as per protocol, whenever possible, up to Day 60. In all cases, the reason for study drug discontinuation will be noted on the CRF. This is in the view of maximizing the number of patients with actual follow-up information and minimizing patients lost to follow-up.

Patients should be withdrawn from the study in the event of any of the following:

- 1. If the patient withdraws consent to participate in the study as a whole;
- 2. If the patient is lost to follow-up.

The patient has the right to withdraw from the study at any time. Nevertheless, investigators will be trained to minimize full withdrawals from study wherever possible. Survival status and the requirement for invasive mechanical ventilation up to Day 60 are absolutely necessary for all randomized participants and should still be reported for participants who withdraw from the study, where permitted by local guidelines. Site staff should make multiple attempts to contact patients who miss a study visit; it is better to have a late visit than a missed visit.

The reason for patient withdrawal from the study will be noted on the CRF. Where applicable, the investigator should attempt to follow patients withdrawn from study until resolution of any adverse events. Upon withdrawal, no further dosing should be performed for these patients. Investigators shall make reasonable attempts to contact lost-to-follow-up patients for evaluation.

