- b. Directed physical examination (symptom- and disease-driven, will not be repeated if assessment done within 2 days from the discharge day);
- c. Body weight with BMI calculated (measured if possible);
- d. From SOC, collect the vital signs including heart rate, respiratory rate, oxygen saturation and body temperature;
- e. COVID-19 symptom check (including but not limited to, fever, myalgia, coughing, smell and taste alteration, headache, gastrointestinal disorders...etc.) as per SOC;
- f. SOC laboratory tests including at a minimum, urinalysis (dipstick), hematology and serum chemistry (will not be repeated if assessment done within 2 days from the discharge day), as per Section 11.2;
- g. Urine (or serum) pregnancy test if applicable;
- h. Health status determination using the 7-point ordinal scale;
- i. Quality-of-Life questionnaire: EQ-5D-5L questionnaire;
- j. If applicable, dispensing to the patient the remaining study drug treatment with instructions for storage in the home refrigerator, self-administration, and return of unused study drug in a prelabeled envelope;
- k. Asking safety-focused open-ended questions:
 - i. How is your health today?
 - ii. How is your vision today?
 - iii. How is your skin today?
- 1. Adverse event verification and follow-up on ongoing adverse events.

4. On all other Days in Hospital until the day before discharge or before Day 14 (Visit numbers = Day of the study): The following assessments will be done:

- a. From SOC, collect the vital signs including heart rate, respiratory rate, oxygen saturation and body temperature (can be done multiple times during each day as part of SOC, but at a minimum twice);
- b. COVID-19 symptom check (including but not limited to, fever, myalgia, coughing, smell and taste alteration, headache, gastrointestinal disorders...etc.) as per SOC;
- c. Health status determination using the 7-point ordinal scale;
- d. Handing study medication for intake during the main meal of the day;
- e. Adverse event verification and follow-up on ongoing adverse events.

5. Early-Termination Visit

This visit may happen anytime a patient elects to withdraw consent or becomes unable to be followed-up, as detailed in Section 8.3. The following assessments can be performed, sometimes indirectly since the patient may not be able to contribute.

- a. Concomitant medication verification, including any supplemental oxygen currently in use, including the oxygen flow;

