9.3.5 Administration of Study Drug Treatment

On each inpatient Day at the Hospital, the patient will be handed the required quantity of capsules to ingest with the main meal of the day (if possible). The capsules should not be broken down to administer their content through a feeding tube if the patient is intubated and cannot ingest anymore the capsules intact. If the patient is discharged from the clinical site before Day 14 (the last day of study drug intake), the patient will be dispensed the remaining capsules of study drug and will receive instructions to continue the intake until Day 14.

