- In the event that a patient gets intubated to start mechanical ventilation, the medications, the procedures and various electrolytes to support life and provide comfort do not need to be entered in the eCRF: Life support therapies and dose adjustments do not need to be reported in the eCRF for mechanically ventilated patients (eg, medications used for continuous sedation and muscle paralysis, fluid and electrolytes management, antibiotics, medications used to correct low blood pressure or hypotensive shock, medications for venous thromboembolism prevention, and procedures for cardiopulmonary resuscitation).

For the SAE report: All con-meds used to manage the SAE, including dosing adjustments should be summarized in the con-med section of the SAE report for a thorough review of the event by the Sponsor and the medical monitor.

Because of the need to report to health authorities all Suspected Unexpected Serious Adverse Reactions (SUSAR) in a timely manner, it is vitally important that an Investigator report immediately any adverse experiences which would be considered serious, even if the Investigator does not consider the adverse experience to be clinically significant or drug related. Should the Investigator become aware of an SAE (regardless of relationship to study drug) that occurs until the last scheduled study follow-up, on Day 60, or until early termination or death, whichever occurs first, the SAE must be reported in accordance with the procedures specified in this protocol.

All SAEs that are not resolved by the end of the study, or that were not resolved upon discontinuation of the patient's participation in the study, are to be followed until the AE resolves, the AE stabilizes, the AE returns to baseline values (if a baseline value is available), or it is shown that the AE is not attributable to the study drug or study conduct. If a patient becomes pregnant during the study, the patient will be removed from the study without receiving further study medication. Follow-up regarding the outcome of the pregnancy and any postnatal sequelae in the infant is required. Pregnancies are considered immediately reportable AEs (within 24 hours of awareness) and are to be documented in the e-CRF.

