11.2 Clinical Laboratory Assessments

Blood and urine samples will be collected according to the Schedule of Events (page 11) and analyzed locally at the clinical site's laboratory as per their SOC. Laboratory test results that are abnormal and considered clinically significant must be reported as AEs (as per Section 11.1.1). Screening laboratory results must be available and reviewed by the Investigator before randomization. The typical safety laboratory test panels are shown in Table 2 below (it is acceptable that SOC varies between clinical sites regarding some tests, but testing must include at the minimum tests evaluating the hematologic status, the kidney and the liver functions. The tests marked by a (+) are suggested:

Table 2: Laboratory Tests Panels

Serum Chemistry	Hematology	Urinalysis*	
Albumin+	Hematocrit+	Nitrite	
Creatinine+	Hemoglobin+	Urobilinogen+	
Total protein	Red blood cells+	Protein+	

Potassium Mean corpuscular hemoglobin pH+
Sodium Mean corpuscular hemoglobin Blood+

Calcium Mean corpuscular volume Leucocyte esterase
Bicarbonate Reticulocytes Specific gravity

PhosphatePlatelet count+KetonesAlkaline phosphatase+Leucocytes+Bilirubin+ALT+Differential (absolute and %)Glucose+AST+EosinophilsAppearance

GGT Basophils
Total bilirubin+ Neutrophils+
Blood urea nitrogen+ Lymphocytes+
Glucose Monocytes

For the purpose of this study conduct, the laboratory tests performed in the local laboratory are the primary tests. Normal ranges and accreditations should be current and filed in the Investigator Site File and in the study's Trial Master File.

In addition, according to the Schedule of Events, pregnancy tests (β -human chorionic gonadotropin) for females of childbearing potential: Urine (or serum) samples will be obtained as specified in the Schedule of Events, page 11 and tested. The urine (or serum) pregnancy test pre-randomization must be negative before the first dose of study drug. Finally, clinical laboratory evaluations may be performed at other times if judged to be clinically appropriate by the Investigator.

Reporting requirements for laboratory tests performed to monitor a SAE, in addition to the protocol-requested safety laboratory tests: Patients experiencing a worsening of their condition (generally a life-threatening situation declared as a SAE) are subject to receiving numerous con-meds, spontaneous treatment adjustments, along with frequent safety laboratory testing.

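### Section 8.3 item 6 exempts in-vitro-fertilization pregnancies from stopping study drug and from the 24-hour report, while Section 11.1.3.1 exempts none; the drug is a retinoid found teratogenic in rats and rabbits

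*Protocol*

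**What the plan says.** Two sections of the protocol govern pregnancy during the study.

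- **Section 8.3, item 6** is in the list of reasons for permanently stopping study drug. Its condition is "If a female patient has a confirmed pregnancy (with the exception of a pregnancy resulting from" in-vitro fertilization). When the condition is met, the site must report within 24 hours of awareness and stop the drug. The item's closing sentence carries no exception: "Pregnancy, whether in a patient or in a partner of a patient should be followed up until conclusion".
- **Section 11.1.3.1**, on serious adverse event reporting, states "If a patient becomes pregnant during the study, the patient will be removed from the study without receiving further study medication", and then "Pregnancies are considered immediately reportable AEs (within 24 hours of awareness) and are to be documented in the e-CRF". It makes no distinction by mode of conception.

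The entry rules make no such distinction either. Exclusion 1 in Section 8.2 bars pregnancy. Inclusion 7 in Section 8.1 requires contraception until 30 days after the last dose. Section 11.2 adds: "The urine (or serum) pregnancy test pre-randomization must be negative before the first dose of study drug".

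After the first dose, the next scheduled pregnancy test is at discharge or Day 14 (Section 9.2.3, third list, item g): "Urine (or serum) pregnancy test if applicable". Item j of the same list is "If applicable, dispensing to the patient the remaining study drug treatment with instructions for storage in the home refrigerator". Section 9.3.5 says of a patient discharged before Day 14 that "the patient will be dispensed the remaining capsules of study drug and will receive instructions to continue the intake until Day 14".

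**The concern.** The parenthesis qualifies the condition, so it removes both consequences: stopping the drug and reporting within 24 hours. It does not tell sites to keep dosing. It does leave these patients off the list that a site would consult to decide whether drug must stop, and it gives no reason. How a pregnancy began does not change the embryo's exposure.

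The hazard is the protocol's own. Section 5.4.1.1 describes fenretinide at 800 mg/kg/day as teratogenic in rats and rabbits, reports complete inhibition of implantation in mice at 100 mg/kg/day, and ties retinoid teratogenicity to the role of retinoic acid in the embryo.

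What is at stake is fetal safety under a stated stopping rule. At the discharge visit the test result and the decision to hand out capsules for home use fall together, and the two sections do not give the same rule for that moment.

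**Working it through.** **Text comparison.** The plan gives no figure on this point, so the check is mainly a reading of the provisions side by side.

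| Provision | Ordinary pregnancy | In-vitro-fertilization pregnancy |
|---|---|---|
| 8.2 exclusion 1; negative test before first dose | Barred | Barred |
| 8.3 item 6: stop drug | Required | Excepted |
| 8.3 item 6: report within 24 hours | Required | Excepted |
| 8.3 item 6: follow to conclusion | Required | Required |
| 8.3 item 3: stop in patient's best interest | Discretionary | Discretionary |
| 11.1.3.1: no further study medication | Required | Required |
| 11.1.3.1: report within 24 hours | Required | Required |

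The sections part in two cells only, and those are the two actions that protect the fetus and inform the sponsor. All of this is current operative text, and no provision ranks one section above the other.

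**Contraception as a barrier.** The methods accepted in Section 8.1 item 7 include abstinence, spermicide with a barrier, and partner sterilization. These prevent conception by intercourse; by themselves they would not prevent a pregnancy from an embryo transfer. By inference, a transfer shortly before admission could be compatible with a negative pre-dose test and a later positive one.

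**Doses at risk if a site relied on 8.3 alone.** Inputs are from Section 9.3: 300 mg on Days 1 to 3 and 200 mg on Days 4 to 14.

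- Full course: 3 × 300 + 11 × 200 = 3,100 mg in 14 doses.
- Assumption: the dose for the day of the positive test has already been taken.
- Doses remaining after a positive test on Day d: 14 − d.

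| Day of positive test | Doses left | Amount left |
|---|---|---|
| 1 (bound) | 13 | 2 × 300 + 11 × 200 = 2,800 mg |
| 2 | 12 | 1 × 300 + 11 × 200 = 2,500 mg |
| 5 | 9 | 9 × 200 = 1,800 mg |
| 8 | 6 | 6 × 200 = 1,200 mg |
| 12 | 2 | 2 × 200 = 400 mg |
| 13 | 1 | 1 × 200 = 200 mg |
| 14 | 0 | 0 mg |

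The Day 1 row is only a bound, since it needs a positive test right after the negative pre-dose one. The later rows correspond to discharge on that day, when the test is scheduled. If the site follows 11.1.3.1, every row is zero.

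**The case against.** The strongest reply is that the protocol already contains the right rule. An exception in one list is silence, not permission. Section 11.1.3.1 is mandatory and unconditional, so a site can satisfy both sections only by stopping drug and reporting. Item 3 of 8.3 and the unqualified follow-up sentence add cover. This is largely right: it limits the consequence and means the sections are not flatly opposed. It does not remove the defect, because the section that sets out when drug must be discontinued is the one with the gap, and the complete rule sits under adverse event reporting.

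The affected population is nearly empty. Entry needs a negative test and contraception, treatment lasts at most 14 days, pilot mean age was about 57 years, and about 60% of pilot patients were male (Section 5.4.2.1). That stands, and so does the remark that the dose counts say nothing about frequency; they show only how much drug the gap could cover.

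The animal finding was at 800 mg/kg/day, against flat doses of 300 then 200 mg here, and Section 5.4.1.1 also cites a hamster screen suggesting fenretinide is less teratogenic than all-trans retinoic acid. Both facts belong in the picture, and no human risk estimate is claimed. Neither gives a reason to treat pregnancies differently by mode of conception.

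Finally, the SAP addendum shows that the database was locked and results first released on 14 March 2024. No patient in this trial can now benefit, so the edit corrects the record and guards against reuse of the wording in a later LAU-7b protocol.

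**Conclusion.** The point holds: item 6 of Section 8.3 is wrong as written. It exempts one class of pregnancy from drug discontinuation and prompt reporting, contrary to Section 11.1.3.1 and to the intent, though not the letter, of the entry criteria, and no reason is given.

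The weight is minor. The event is very rare, and the possible extra exposure runs from none (11.1.3.1 followed, or test on Day 14) through 1,800 mg for a positive discharge test on Day 5 to a bound of 2,800 mg. Those amounts assume that the test day's dose was taken and that the site acted on 8.3 alone. The point still merits correction, because the possible harm is to a fetus and may be irreversible while the correction costs almost nothing. It has no bearing on endpoints, alpha, power or sample size.

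**What to change.** Delete the in-vitro-fertilization parenthesis from Section 8.3 item 6, so that every confirmed pregnancy in a patient leads to drug discontinuation and a 24-hour report.

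In the same edit, settle a related but separate mismatch. Section 11.1.3.1 removes a pregnant patient from the study, whereas Section 8.3 limits study withdrawal to withdrawn consent or loss to follow-up and keeps patients who stop drug under assessment to Day 60 if they agree. Section 11.1.3.1 should say that the patient stops study drug and stays in follow-up, which also protects collection of the Day 60 outcome.

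The cost is one deleted parenthesis and a few changed words in a protocol amendment, or in the template if the wording is reused. The visit schedule and the analysis do not change.
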